10.11.6. Substudy A Design

10.11.6.1. Overall Design

This is a Phase 1/2 randomized, parallel-group, observer-blinded substudy to describe the safety, tolerability, and immunogenicity of a combined RSVpreF and bivalent BNT162b2 (original/Omi BA.4/BA.5) vaccine [RSVpreF+BNT162b2], administered concomitantly with a seasonal influenza vaccine or administered alone. Approximately 1050 healthy participants ≥ 65 years of age will be enrolled in Substudy A.

Note: "Enrolled" means a participant's, or their legally authorized representative's, agreement to participate in a clinical study following completion of the informed consent process.

Randomization will be conducted across 2 enrollment strata (see Table 4).

Table 4. Substudy A Enrollment Strata

Enrollment Stratum	Total Number of Participants	Number of Participants per Vaccine Group	Vaccine Group Number	Vaccine Group Description
1	750	150	1	[RSVpreF+BNT162b2] administered concurrently in the opposite arm to licensed QIV
		150	2	[RSVpreF+BNT162b2] administered concurrently in the opposite arm to placebo
		150	3	Bivalent BNT162b2 administered concurrently in the opposite arm to placebo
		150	4	RSVpreF administered concurrently in the opposite arm to placebo
		150	5	Licensed QIV administered concurrently in the opposite arm to placebo
2	300	150	6	RSVpreF and bivalent BNT162b2 (2 injections in the same arm) coadministered concurrently in the opposite arm to placebo
		150	7	RSVpreF and bivalent BNT162b2 (2 injections in the same arm) coadministered concurrently in the opposite arm to QIV

All participants will be asked to complete a reactogenicity e-diary for 7 days following vaccination. Blood samples of approximately 50 mL will be collected for immunogenicity assessments prior to vaccination at Visit A101 and 1 month after vaccination (Visit A102).

E-diary data from Day 1 through Day 3 for the first 50 participants in Groups 1 to 5, and the first 20 participants in Groups 6 and 7, will be evaluated prior to enrollment of the remaining participants in each group.

AEs and SAEs will be collected from the signing of informed consent through Visit A102 (1-month follow-up visit). SAEs will be collected from the signing of informed consent through Visit A103 (6-month telephone contact).

Substudy A will have stopping rules that will apply to participants as detailed in [Section 10.11.10.5](#), with monitoring by designated unblinded sponsor site staff on an ongoing basis. If a stopping rule is confirmed, further randomization and study intervention administration will be paused while additional information is gathered, and cumulative unblinded safety data will be reviewed by the IRC. Participants who have received study intervention will continue further study visits and procedures as scheduled. A charter for the IRC will be prepared and finalized before the first participant provides informed consent.

The total duration of the study for each participant will be up to approximately 6 months.

10.11.6.2. Scientific Rationale for Study Design

See [Section 2.1](#).

10.11.6.3. Justification for Dose

See [Section 4.3](#).

10.11.6.4. End of Study Definition

See [Section 4.4](#).

10.11.7. Substudy A Population

10.11.7.1. Substudy A Inclusion Criteria

Participants are eligible to be included in Substudy A only if all of the following criteria apply:

Age and Sex:

1. Male or female participants ≥ 65 years of age at Visit 1 (Day 1).
 - Refer to [Section 10.4](#) for reproductive criteria for male [Section 10.4.1](#) and female ([Section 10.4.2](#)) participants.

Disease Characteristics:

NA.

Other Inclusion Criteria:

2. Participants who are willing and able to comply with all scheduled visits, investigational plan, laboratory tests, lifestyle considerations, and other study procedures.
3. Healthy participants who are determined by medical history, physical examination (if required), and clinical judgment of the investigator to be eligible for inclusion in the study.

Note: Healthy participants with preexisting stable disease, defined as disease not requiring significant change in therapy or hospitalization for worsening disease during the 6 weeks before enrollment, can be included. Specific criteria for participants with known stable infection with HIV, HCV, or HBV can be found in [Section 10.9](#).

4. Capable of giving signed informed consent as described in the protocol, which includes compliance with the requirements and restrictions listed in the ICD and in this protocol.
5. Participants who have received at least 3 prior US-authorized mRNA COVID-19 vaccines, with the last dose being an updated (bivalent) vaccine given at least ≥ 150 days before Visit A101 (Day 1). Any dose of modRNA SARS-CoV-2 vaccine received after 01 September 2022 in the US may be considered to be a bivalent vaccine.

Note: Documented confirmation of prior doses of COVID-19 vaccines received must be obtained prior to randomization.

10.11.7.2. Substudy A Exclusion Criteria

Participants are excluded from Substudy A if any of the following criteria apply:

Medical Conditions:

1. A confirmed diagnosis of COVID-19, RSV infection, or influenza ≤ 120 days before study intervention administration.
2. History of severe adverse reaction associated with any vaccine and/or severe allergic reaction (eg, anaphylaxis) to any component of the study intervention(s).
3. Immunocompromised individuals with known or suspected immunodeficiency, as determined by history and/or laboratory/physical examination.
4. Bleeding diathesis or condition associated with prolonged bleeding that would, in the opinion of the investigator, contraindicate intramuscular injection.
5. Allergy to egg proteins (egg or egg products) or chicken proteins.

6. Any medical or psychiatric condition including recent (within the past year) or active suicidal ideation/behavior or laboratory abnormality that may increase the risk of study participation or, in the investigator's judgment, make the participant inappropriate for the study.

Prior/Concomitant Therapy:

7. Receipt of chronic systemic treatment with known immunosuppressant medications (including cytotoxic agents or systemic corticosteroids), or radiotherapy, within 60 days before enrollment through conclusion of the study.

Note: Systemic corticosteroids are defined as those administered for ≥ 14 days at a dose of ≥ 20 mg/day of prednisone or equivalent (eg, for cancer or an autoimmune disease). Inhaled/nebulized, intra-articular, intrabursal, or topical (skin or eyes) corticosteroids are permitted.

8. Receipt of blood/plasma products, immunoglobulin, or monoclonal antibodies, from 60 days before study intervention administration, or planned receipt throughout the study.
9. Receipt of any RSV vaccine at any time prior to enrollment, or planned receipt throughout the study.
10. Receipt of any influenza vaccine ≤ 120 days before study enrollment.

Prior/Concurrent Clinical Study Experience:

11. Participation in other studies involving a study intervention within 28 days before randomization.
12. Anticipated participation in other studies within 28 days after receipt of study intervention in this study.

Diagnostic Assessments:

NA.

Other Exclusion Criteria:

13. Investigator site staff directly involved in the conduct of the study and their family members, site staff otherwise supervised by the investigator, and sponsor and sponsor delegate employees directly involved in the conduct of the study and their family members.

10.11.7.3. Criteria for Temporarily Delaying Enrollment/Randomization/Administration of Study Intervention

The following conditions may allow a participant to be randomized once the conditions have resolved and the participant is otherwise considered eligible. Participants meeting these criteria at Visit 1 will be considered screen failures if enrollment has closed once the condition(s) has/have resolved.

1. A positive SARS-CoV-2 test result (NAAT or rapid antigen test) within the previous 28 days.
2. Current febrile illness (oral temperature $\geq 38.0^{\circ}\text{C}$ [$\geq 100.4^{\circ}\text{F}$]) or other acute illness within 48 hours before study intervention administration. This includes symptoms that could represent a potential COVID-19 illness (refer to [Section 8.4.8](#)).

Note: The participant should be directed to seek additional testing through their primary healthcare provider at a licensed clinical laboratory when exhibiting potential COVID-19 symptoms or otherwise receiving a positive result and counseled on whether to take any precautionary measures pending confirmatory testing, as per local guidance.

3. Receipt of any nonstudy vaccine within 28 days before study intervention administration at Visit A101.
4. Anticipated receipt of any nonstudy vaccine within 28 days after study intervention administration at Visit A101.
5. Receipt of short-term (<14 days) systemic corticosteroids. Study intervention administration should be delayed until systemic corticosteroid use has been discontinued for at least 28 days. Inhaled/nebulized, intra-articular, intrabursal, or topical (skin or eyes) corticosteroids are permitted.

10.11.8. Substudy A Intervention and Concomitant Therapy

Study interventions are all prespecified investigational and medical devices, and other interventions (eg, surgical and behavioral), intended to be administered to the study participants during the study conduct.

- Combined RSVpreF and bivalent BNT162b2 (original*/Omi BA.4/BA.5) vaccine [RSVpreF+BNT162b2] 0.8 mL, which is a combination of the following:
 - 120 μg RSVpreF containing 2 stabilized RSV prefusion F antigens, in equal amounts (60 μg per strain) from virus subgroups A and B
 - 30 μg Bivalent BNT162b2 (15 μg original/Omi BA.4/BA.5), which contains original BNT162b2 and BNT162b2 Omicron (15 μg B.1.1.529 sublineage BA.4/BA.5)

- 120 µg RSVpreF containing 2 stabilized RSV prefusion F antigens, in equal amounts (60 µg per strain) from virus subgroups A and B
- Licensed QIV
- 30 µg Bivalent BNT162b2 (15 µg original/Omi BA.4/BA.5), which contains original BNT162b2 and BNT162b2 Omicron (15 µg B.1.1.529 sublineage BA.4/BA.5)
- Normal saline (0.9% sodium chloride solution for injection) 0.8 mL

*Original refers to the ancestral strain (Wuhan-Hu-1; USA-WA1/2020), also referred to in this protocol as the reference strain.

10.11.8.1. Study Intervention(s) Administered

Study interventions for Substudy A will include the following:

Substudy A Study Interventions					
Intervention Name	Combination [RSVpreF+BNTb162b2]	Bivalent BNT162b2 (Original ^a /Omi BA.4/BA.5)	RSVpreF	QIV	Normal Saline Placebo
Arm Name (group of participants receiving a specific study intervention or no study intervention)	Groups 1, 2: Combination [RSVpreF+BNT162b2]	Groups 3, 6, 7: Bivalent BNT162b2 (original ^a /Omi BA.4/BA.5) (30 µg)	Groups 4, 6, 7: RSVpreF (120 µg)	Groups 1, 5, 7: QIV	Groups 2, 3, 4, 5, 6: Placebo
Targeted Influenza Strains	NA	NA	NA	For each season, strains as recommended by WHO	NA
Type	Vaccine	modRNA vaccine	Vaccine	Vaccine	Placebo
Dose Formulation	Suspension for injection	Suspension for injection	Powder for solution for injection	Suspension for injection	Normal saline (0.9% sodium chloride solution for injection)
Unit Dose Strength(s)	As detailed in the IPM	As detailed in the IPM	As detailed in the IPM	As detailed in the IPM	NA
Dosage Level(s) or Volume	RSVpreF 120 µg Bivalent BNT162b2 30 µg	30 µg	120 µg	0.7 mL	0.8 mL
Route of Administration	Intramuscular injection	Intramuscular injection	Intramuscular injection	Intramuscular injection	Intramuscular injection
Use	Experimental	Comparator (Group 3) Experimental (Groups 6 and 7)	Comparator (Group 4) Experimental (Groups 6 and 7)	Comparator (Group 5) Experimental (Groups 1 and 7)	Placebo for blinding
IMP or NIMP/AxMP	IMP	IMP	IMP	IMP	IMP
Sourcing	Provided centrally by Pfizer	Provided centrally by Pfizer	Provided centrally by Pfizer	Provided centrally by Pfizer	Provided centrally by Pfizer

PFIZER CONFIDENTIAL

CT02-GSOP Clinical Protocol Template Phase 1 2 3 4 (14 April 2023)

TMF Doc ID: 164.01

Page 103

Substudy A Study Interventions					
Intervention Name	Combination [RSVpreF+BNTb162b2]	Bivalent BNT162b2 (Original ^a /Omi BA.4/BA.5)	RSVpreF	QIV	Normal Saline Placebo
Packaging and Labeling	Study intervention will be generated by mixing the following at the site at the dose-level combinations detailed below: 
 • RSVpreF • Bivalent BNT162b2 (original^a/Omi BA.4/BA.5) Each vial will be labeled per country requirement.	Study intervention will be provided in a glass vial as open-label supply. Each vial will be labeled per country requirement.	Study intervention will be provided in a glass vial as open-label supply. It is reconstituted with a PFS of sterile water diluent for injection (supplied). Each vial and PFS will be labeled per country requirement.	Study intervention will be provided as a PFS as open-label supply. Each carton will be labeled per country requirement.	Study intervention will be provided as either a PFS or a glass/plastic vial as open-label supply. Each PFS or vial will be labeled per country requirement.
SRSD	IB	IB	IB	USPI	NA

a. Original refers to the ancestral strain (Wuhan-Hu-1; USA-WA1/2020).

Substudy A Study Arms							
Group Number	1	2	3	4	5	6	7
Arm Title	Combination [RSVpreF+BNT162b2 (0.8 mL)] + QIV	Combination [RSVpreF+BNT162b2 (0.8 mL)] + placebo	Bivalent BNT162b2 (30 µg) + placebo	RSVpreF (120 µg) + placebo	QIV + placebo	Coadministration RSVpreF + bivalent BNT162b2 + placebo	Coadministration RSVpreF + bivalent BNT162b2 + QIV
Arm Type	Experimental	Experimental	Comparator	Comparator	Comparator	Experimental	Experimental
Arm Description	Participants will receive combination [RSVpreF (120 µg) + BNT162b2 (30 µg)] + QIV	Participants will receive combination [RSVpreF (120 µg) + BNT162b2 (30 µg)] + placebo	Participants will receive BNT162b2 (30 µg) + placebo	Participants will receive RSVpreF (120 µg) + placebo	Participants will receive QIV + placebo	Participants will receive coadministered RSVpreF (120 µg) + BNT162b2 (30 µg) + placebo	Participants will receive coadministered RSVpreF (120 µg) + BNT162b2 (30 µg) + QIV

PFIZER CONFIDENTIAL

CT02-GSOP Clinical Protocol Template Phase 1 2 3 4 (14 April 2023)

TMF Doc ID: 164.01

Page 104

Substudy A Study Arms							
Group Number	1	2	3	4	5	6	7
Associated Intervention Labels	[RSVpreF (120 µg) + BNT162b2 (30 µg)] + QIV	[RSVpreF (120 µg) + BNT162b2 (30 µg)] + placebo	BNT162b2 (30 µg) + placebo	RSVpreF (120 µg) + placebo	QIV + placebo	RSVpreF (120 µg) + BNT162b2 (30 µg) + placebo	RSVpreF (120 µg) + BNT162b2 (30 µg) + QIV

10.11.8.1.1. Administration

See [Section 10.11.8.1](#).

During Substudy A, all study interventions are to be administered as an intramuscular injection into the deltoid muscle of the arm, in accordance with the schema ([Section 10.11.2](#)) and the SoA ([Section 10.11.3](#)).

10.11.8.1.2. Medical Devices

See [Section 6.1.2](#).

10.11.8.1.3. Preparation, Handling, Storage, and Accountability

See [Section 6.2](#).

10.11.8.1.3.1. Preparation and Dispensing

See [Section 6.2.1](#).

During Substudy A, study intervention will be prepared and dispensed by an unblinded appropriately qualified and experienced member of the study staff (eg, physician, nurse, physician's assistant, nurse practitioner, pharmacy assistant/technician, or pharmacist) as allowed by local, state, and institutional guidance. A second unblinded staff member will verify the dispensing.

10.11.8.1.4. Allocation to Study Intervention

See [Section 6.3](#).

Allocation of study intervention at Visit A101 in Substudy A will be conducted via the IRT.

E-diary data from Day 1 through Day 3 for the first 50 participants in Groups 1 to 5, and the first 20 participants in Groups 6 and 7, will be evaluated prior to enrollment of the remaining participants in each group. Initial enrollment will be controlled through the IRT system to manage this approach.

10.11.8.2. Blinding

This is an observer-blinded study.

10.11.8.2.1. Blinding of Participants

Participants will be blinded to their assigned study intervention. When the 1-month analysis has been performed, and when directed by the sponsor (anticipated to be between Visit A102 and Visit A103), participants may be unblinded to confirm the vaccine received. The study team will also become unblinded to the participant's study intervention allocation at this time.

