10.11.5. Objectives, Endpoints, and Estimands – Substudy A

Substudy A (Phase 1/2)		
Objectives	Estimands	Endpoints
Primary	Primary	Primary
To describe the safety and tolerability of [RSVpreF+BNT162b2]	
In participants receiving study intervention, the percentage of participants reporting:
 
 Local reactions within 7 days following vaccination Systemic events within 7 days following vaccination AEs from vaccination through 1 month after vaccination SAEs from vaccination through 6 months after vaccination 	
 Local reactions (pain at the injection site, redness, and swelling) Systemic events (fever, fatigue, headache, chills, vomiting, diarrhea, new or worsened muscle pain, and new or worsened joint pain) AEs SAEs
To demonstrate that the immune responses elicited by [RSVpreF+BNT162b2] when coadministered with QIV are noninferior to those elicited by each vaccine alone: 
 RSVpreF alone (Group 1 vs Group 4) Bivalent BNT162b2 alone (Group 1 vs Group 3) QIV alone (Group 1 vs Group 5) 	
 In participants in compliance with the key protocol criteria (evaluable participants for Groups 1 and 4): 
 GMR of NTs at 1 month after vaccination in Group 1 to Group 4 for RSV subgroup A GMR of NTs at 1 month after vaccination in Group 1 to Group 4 for RSV subgroup B In participants in compliance with the key protocol criteria (evaluable participants for Groups 1 and 3): 
 GMR of NTs at 1 month after vaccination in Group 1 to Group 3 for SARS-CoV-2 Omicron BA.4/BA.5 GMR of NTs at 1 month after vaccination in Group 1 to Group 3 for SARS-CoV-2 reference strain In participants in compliance with the key protocol criteria (evaluable participants for Groups 1 and 5): 
 GMR of HAI titers at 1 month after vaccination in Group 1 to Group 5 for each influenza strain included in the QIV 	
 RSV A and RSV B NTs SARS-CoV-2 Omicron BA.4/BA.5 and reference-strain NTs HAI titers for each strain contained in the QIV

PFIZER CONFIDENTIAL

CT02-GSOP Clinical Protocol Template Phase 1 2 3 4 (14 April 2023)

TMF Doc ID: 164.01

Page 94

Substudy A (Phase 1/2)		
Objectives	Estimands	Endpoints

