10.11.8.2.2. Blinding of Site Personnel

The study staff receiving, storing, dispensing, preparing, and administering the study interventions will be unblinded. All other study and site personnel, including the investigator and investigator staff, will be blinded to assignment of study intervention. In particular, the individuals who evaluate participant safety will be blinded. Because there are differences in physical appearance between study interventions, study interventions will be administered in a manner that prevents the participants from identifying the study intervention based on its appearance.

The PI will assign the responsibility of the unblinded dispensers/administrators to persons who will not participate in the evaluation of any study participant. To ensure adequate coverage, at least 2 unblinded dispensers/administrators will be assigned per site. Members of the study site nursing/medical staff or clinic pharmacy will fulfill these roles. Contact between the unblinded dispensers and study participants should be kept to a minimum. The investigator, study coordinator, and any site staff other than the unblinded dispensers/administrators must not be allowed to know the study intervention assigned to any study participant and must not be allowed to see the study intervention container contents.

In the event of a Quality Assurance audit, the auditor(s) will be allowed access to unblinded study intervention records at the site(s) to verify that randomization/dispensing has been done accurately.

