- The investigator or appropriately qualified designee reviews the reactogenicity e-diary data online following vaccination to evaluate participant compliance and as part of the ongoing safety review. Daily review is optimal during the active diary period.

10.11.10.7.2. Visit A102 – 1-Month Follow-Up Visit (After Vaccination) – 28 to 35 Days After Visit A101

- Record AEs as described in [Section 8.4](#).
- Record nonstudy vaccinations as described in [Section 10.11.8.7](#).
- Record prohibited medication use as described in [Section 10.11.8.7.1](#).
- Verify understanding of and compliance with protocol requirements for contraception as described in [Section 5.3.1](#).
- Collect a blood sample of approximately 50 mL for immunogenicity testing.
- Review the participant's reactogenicity e-diary data. Collect stop dates of any reactogenicity e-diary events ongoing on the last day that the reactogenicity e-diary was completed and record stop dates in the CRF if required.
- If not already completed, collect the participant's e-diary or assist the participant with removing the study application from their own personal device.
 - Ensure all e-diary data have been transferred prior to e-diary deactivation or removal of the app.
- Record any AEs that occur within the 48 hours after the blood draw as described in [Section 8.4.1](#).

10.11.10.7.3. Visit A103 – 6-Month Telephone Contact – 175 to 189 Days After Visit A101

- Contact the participant by telephone.
- Record SAEs as described in [Section 8.4](#).
- Record nonstudy vaccinations as described in [Section 10.11.8.7](#).
- Record prohibited medication use as described in [Section 10.11.8.7.1](#).

- Complete the source documents.
- The investigator or an authorized designee completes the CRFs.

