10.11.11.4. Interim Analyses

No formal interim analysis will be conducted for this study phase.

The primary analysis will be performed on safety and immunogenicity data through 1 month after vaccination (ie, Visit A102); all type I error will be spent at this analysis. Once this analysis has been completed, study participants and the study team may be unblinded to study intervention allocation.

6-Month safety data will be summarized when they become available.

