2.2.1.3.3. SAE Estimands

SAE estimands have the same attributes (treatment condition, population, intercurrent events, population-level summary) as AE estimands ([Section 2.2.1.3.2](#)), except:

- **Variables:** Any SAEs reported throughout 6 months after vaccination ([Section 3.1.2.3](#)).

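### Unblinding is anticipated before Visit A103, the only scheduled SAE inquiry after Visit A102, and the plan does not separate 6-month SAEs collected and judged under blind from the rest

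*Protocol*

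**What the plan says.** Protocol 10.11.8.2.1 ties unblinding to completion of the 1-month analysis and a direction from the sponsor. At that point "participants may be unblinded to confirm the vaccine received", and the timing is "anticipated to be between Visit A102 and Visit A103". It adds: "The study team will also become unblinded to the participant's study intervention allocation at this time". Protocol 10.11.8.2.3 repeats both statements. Protocol 10.11.11.4 is permissive for both parties: "Once this analysis has been completed, study participants and the study team may be unblinded to study intervention allocation". SAP 7.1.1 says the same.

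On site staff, Protocol 10.11.8.2.2 says: "In particular, the individuals who evaluate participant safety will be blinded". It gives no end date. Only the serology laboratory staff are described, in 10.11.8.2.3, as blinded for the whole study.

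The endpoint at issue is a primary safety endpoint. Protocol 10.11.5 lists "SAEs from vaccination through 6 months after vaccination", and SAP 2.2.1.3.3 defines the variable as "Any SAEs reported throughout 6 months after vaccination". The safety objective is descriptive. SAP 2.2.1.3 uses a treatment-policy strategy, and SAP 6.1.4 reports SAEs by vaccine group with no division at unblinding.

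The schedule in Protocol 10.11.3 has three contacts: A101, A102 ("28 to 35 Days After Visit A101") and A103, a telephone call 175 to 189 days after A101.

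**The concern.** Two parts of SAE data involve judgment: what the participant mentions when asked, and whether the investigator calls the event related. Protocol 10.3.3 leaves causality to the investigator's clinical judgment, and SAP 6.1.4.1 allows the bar charts to be divided by relatedness. If the only scheduled inquiry after A102 takes place once the participant, and possibly the assessor, knows who received the new combination, both parts can be influenced by that knowledge. This includes SAEs that began while the blind was intact but were not mentioned until A103.

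A participant who learns that no RSV vaccine was given (Groups 3 and 5) may also seek one, so exposure late in follow-up may differ by group. The planned tables would not show which SAEs were collected under blind.

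**Working it through.** The plan states no figure for this point, so there is none to reproduce. The check is arithmetic on visit windows, followed by a comparison of the blinding texts.

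**Inputs** (Protocol 10.11.3, 10.11.10.7.2 and 10.11.10.7.3): A102 on day 28 to 35; A103 on day T = 175 to 189; no scheduled contact between them.

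**1. Gap covered only by the A103 inquiry**

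- Shortest gap: 175 − 35 = 140 days; 140/175 = 80.0% of the window.
- Longest gap: 189 − 28 = 161 days; 161/189 = 85.2% of the window.

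This is the stretch first covered by scheduled questioning at A103, whatever the unblinding day, provided that unblinding comes before A103.

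**2. Share of the window spent unblinded**, if unblinding falls on day u: (T − u)/T.

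| u | T = 175 | T = 189 |
|---|---|---|
| 35 | 80% | 81.5% |
| 60 | 65.7% | 68.3% |
| 90 | 48.6% | 52.4% |
| 120 | 31.4% | 36.5% |
| 150 | 14.3% | 20.6% |

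The share exceeds one half only if u is below T/2, which is day 87.5 to 94.5. The documents do not give u.

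**3. Illustration with assumed calendars.** Assume uniform enrollment over E = 14, 28, 56 or 84 days, unblinding of everyone L = 14, 30, 60 or 90 days after the last A102 (taken at day 35), and A103 on day 182. A participant enrolled on day x is then unblinded on own day E + 35 + L − x.

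- Fastest case (E = 14, L = 14): own days 49 to 63, mean 56; mean share unblinded (182 − 56)/182 = 69%.
- Slowest case (E = 84, L = 90): own days 125 to 209. A103 follows unblinding for (182 − 125)/84 = 68% of participants, and the mean share over all participants is 0.679 × (57/2)/182 = 11%.
- In the other 15 of the 16 combinations, A103 follows unblinding for every participant.

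So A103 usually falls after unblinding under these assumptions, while the mean time spent unblinded runs from 11% to 69%.

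**4. The blinding texts side by side**

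- 10.11.8.2.1 and 10.11.8.2.3 say that the study team will be unblinded; 10.11.11.4 says that it may be. None of them defines the study team.
- 10.11.8.2.2 keeps the investigator and the safety evaluators blinded but does not say until when.
- SAP 7.1.2, on blinding, deals only with the barcode listings for assay testing.

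A site cannot tell from these texts whether the investigator who judges an SAE at A103 should still be blinded. In any case, an unblinded participant can reveal the allocation during the call.

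**The case against.** The strongest reply is that this is an openly stated choice with limited reach. The 6-month safety data are summarized descriptively, and all type I error is spent at the 1-month analysis. The immunogenicity hypotheses, reactogenicity, 1-month AEs and the 28-day stopping rules precede the anticipated unblinding. That stands. The one planned group comparison that could touch the gap is the Tier 1 analysis in SAP 6.6.1. Its Guillain-Barré and polyneuropathy windows run to Day 43, which is 42 days after vaccination and so 7 to 14 days past A102.

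SAEs also need not wait for A103. Protocol 10.11.10.7.1 has participants asked at A101 to contact the site about medically attended events and hospitalizations. Protocol 8.4.1.1 requires reporting within 24 hours of awareness, and 10.3.3 requires a causality assessment before the first transmission. Criteria such as death and hospitalization are fairly objective. SAEs reported spontaneously before unblinding are therefore collected and judged under blind. This narrows the point to SAEs not yet reported, but does not remove it.

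Three stronger readings are tempting, and the documents do not support them:

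- A reader might infer that 80% to 85% of the endpoint is unblinded. That figure is calendar time between scheduled contacts. It is neither time unblinded nor a share of SAEs, and the documents give no SAE rates.
- A reader might infer a flat contradiction between 10.11.8.2.2 and 10.11.8.2.1. The former can be read as the general rule and the latter as a timed exception, so this is an ambiguity.
- A reader might infer that a single 6-month rate per group is wrong because later nonstudy vaccines mix in. The treatment-policy estimand calls for that rate, nonstudy vaccines are recorded through A103, and the specific limits on coronavirus, influenza and RSV vaccines in 10.11.8.7.1 end on 31 August 2023 regardless of unblinding. The split proposed here supplements the total.

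**Conclusion.** The concern holds in a limited form. SAEs that arise in the 140 to 161 days between A102 and A103 and are not reported spontaneously may be elicited, and their causality judged, with allocation known. The exposure lies mainly in elicitation and causality. Its size in events cannot be stated, and its size in time depends on an unblinding day that is not given.

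The conclusion assumes that the sponsor does direct unblinding before A103, which the protocol anticipates but does not require, and that at least some participants are told. Whether the site investigator formally becomes unblinded is unclear from the text. The change is a worthwhile, inexpensive improvement; it corrects no error in the main analyses.

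**What to change.** 1. In Protocol 10.11.8.2.1 and 10.11.8.2.3, require that before allocation is disclosed to a participant, by whatever route, the site asks about and records SAEs and nonstudy vaccines to date, and the investigator enters causality. Keep the A103 inquiry for everyone, so that ascertainment stays complete in those who are not unblinded.
2. Record in the CRF the date on which the participant and, if applicable, the investigator was unblinded. Protocol 6.4.4 already requires such a date for emergency unblinding.
3. In SAP 6.1.4, show SAEs before and after unblinding, by onset and by report date, beside the planned treatment-policy 6-month total.
4. Reconcile 10.11.8.2.2 with 10.11.8.2.1 and 10.11.8.2.3: state whether the study team includes the site safety evaluators, and how long they stay blinded.

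The cost is protocol and SAP wording, a few questions before disclosure, one CRF date (a second if the investigator is unblinded) and one table split. No one is denied knowledge of the vaccine received. The documents do not describe how disclosure is made, so it is an assumption that some contact takes place at which the questions can be asked; if none is planned, that contact is an added cost.
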